3.5 Pharmacodynamic and Pharmacokinetic Assessment

The PD and PK endpoints include the following:

- Change and percentage change from baseline in CRP and D-dimer;
- Change and percentage change from baseline in systemic biomarkers of vascular leakage and inflammation (ie, Angpt-2, IL-6, IL-8, TNF α , and HMGB-1);
- Summary of plasma concentrations of biomarkers at each sampling time point for each treatment group; and
- Summary of plasma razuprotafib concentrations for the samples collected on Day 1 and Day 6.

PD and PK endpoints will be summarized descriptively by treatment group using ITT population and PK population.

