9.2.2 Pharmacodynamic Analysis

Pharmacodynamic endpoints will be summarized descriptively.

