2 STUDY OVERVIEW

2.1 Study Objectives

2.1.1 *Primary Objective*

The primary objectives of this study are to assess the safety and efficacy of razuprotafib in subjects with moderate to severe COVID-19.

2.1.2 *Secondary Objectives*

The secondary objectives of this study are to examine the effects of razuprotafib on biomarkers of inflammation and coagulopathy (ie, C-reactive protein [CRP] and D-dimer) in the plasma of subjects with moderate to severe COVID-19 and to characterize exposure of razuprotafib based on plasma concentrations for the samples collected on Day 1 and Day 6.

[figure not shown]
2.1.3 *Exploratory Objectives*

The exploratory objective of this study is to examine the effects of razuprotafib on biomarkers of vascular leakage and inflammation (ie, Angpt-2, IL-6, IL-8, tumor necrosis factor alpha [TNF α], and high mobility group box 1 [HMGB-1]) in the plasma of subjects with moderate to severe COVID-19.

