3 STATISTICAL METHODOLOGY

3.1 General Considerations

3.1.1 *Analysis Day*

Analysis day will be calculated from the date of first dose of study drug. The day of the first dose of study drug will be Day 1, and the day immediately before Day 1 will be Day -1. There will be no Day 0.

3.1.2 *Definition of Baseline*

Baseline is defined as the last measurement prior to the first dose of study drug.

3.1.3 *Visit Windows*

No analysis visit windows will be defined for this study, i.e., the nominal visits /time-points will be used for all statistical summaries/analyses.

3.1.4 *Summary Statistics*

Categorical data will generally be summarized with counts and percentages of subjects. The denominator used for the percentage calculation will be clearly defined. Continuous data will generally be summarized with descriptive statistics including n (number of non-missing values), mean, median, standard deviation, minimum, and maximum.

Summaries of change from baseline variables will include only patients who have both a baseline value and corresponding value at the post-baseline time point of interest.

3.1.5 *Hypothesis Testing*

All statistical comparisons will be made using two-sided tests at $\alpha = 0.05$. All null hypotheses will be of no treatment difference, and all alternative hypotheses will be two-sided. Confidence intervals will be two-sided, unless stated otherwise.

3.1.6 *Handling of Dropouts and Missing Data*

For all efficacy endpoints that do not include death as a possible outcome, data from subjects who die prior to Day 28 will be imputed at Day 28 based on the worst outcome. Other missing data for selected endpoints will be imputed using the methods as described in Section 3.4.

In cases of missing or incomplete dates (e.g. AE and concomitant medications), the missing component(s) will be assumed as the most conservative value possible. For example, AEs with missing start dates, but with stop dates either overlapping into the treatment period or missing,

will be counted as treatment-emergent, taking the worst-case approach. When partial dates are present in the data, both a partial start date and/or a partial stop date will be evaluated to determine whether it can be conclusively established that the AE started prior to the start of study drug or ended prior to the start of study drug. If the above cannot be conclusively established based on the partial and/or present dates, then the AE will be considered as treatment-emergent.

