6 CHANGES FROM PROTOCOL-SPECIFIED STATISTICAL ANALYSES

The protocol does not include the following three endpoints: proportion of subjects alive and not requiring invasive mechanical ventilation at any time through Day 28, time to reach grade 6, 7 or 8 on the NIAID 8-point ordinal scale, and length of hospitalization and not requiring invasive mechanical ventilation from baseline to Day 7 and baseline to Day 28 or death, these have been included in the SAP. The following two endpoints have been deleted from SAP: length of ICU stay from baseline to Day 28 or death has been deleted from SAP and length of hospitalized and free of respiratory failure from baseline to Day 7 and baseline to Day 28 or death.

The protocol does not include percentage change for PD endpoints, this has been included in the SAP.

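### Effects on CRP and D-dimer are a secondary objective, but the plan only describes each arm: no placebo-referenced estimate, interval, baseline adjustment or log-scale analysis

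*SAP*

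**What the plan says.** SAP 2.1.2 makes it a secondary objective "to examine the effects of razuprotafib on biomarkers of inflammation and coagulopathy", naming CRP and D-dimer. Protocol 2.2 says the same. The other five markers (Angpt-2, IL-6, IL-8, TNF alpha and HMGB-1) fall under the exploratory objective in SAP 2.1.3.

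For CRP and D-dimer, SAP 3.5 lists "Change and percentage change from baseline in CRP and D-dimer", and the other five markers get the same treatment. The method is one sentence: "PD and PK endpoints will be summarized descriptively by treatment group using ITT population and PK population". Protocol 9.2.2 agrees: "Pharmacodynamic endpoints will be summarized descriptively". Percentage change is a deliberate SAP addition, recorded in SAP 6: "The protocol does not include percentage change for PD endpoints, this has been included in the SAP".

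The general rule in SAP 3.1.4 fills in which statistics appear: "Continuous data will generally be summarized with descriptive statistics including n (number of non-missing values), mean, median, standard deviation, minimum, and maximum". The same section limits change summaries to subjects who have both a baseline and the relevant later value.

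SAP 3.4.1 treats continuous efficacy endpoints differently. They get a model with treatment, baseline value and disease severity, and a 95% CI and p-value for razuprotafib against placebo. SAP 3.4 adds a comparison of pooled doses with placebo. Neither is extended to the biomarkers.

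**The concern.** In a randomised placebo-controlled trial, the effect of the drug is a contrast with placebo. Change within an arm mixes that effect with the natural course of COVID-19 in hospital and with background therapy such as remdesivir and dexamethasone, which Protocol 5.6.2 permits. The planned tables leave the reader to compare arms by eye, with no measure of uncertainty and no adjustment for chance baseline differences. With about 10 subjects per arm in each step of Part 1 and about 40 per arm in Part 2 under 1:1:1 allocation, such differences can matter.

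A second, smaller issue is scale. Percentage change in a positive marker cannot fall below -100% but has no upper limit. If the distribution is right-skewed, a few large rises can pull the arm mean upward while the typical subject improves.

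**Working it through.** **Inputs.** The documents give no power, effect size or variance for any biomarker, so there is no planned figure to reproduce. The Part 2 arm size follows from SAP 2.2.2: 120/3 = 40 under 1:1:1, or 80 and 40 under 2:1. The SD of the log ratio of follow-up to baseline, *s*, is assumed and varied.

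**1. Mean percentage change within an arm.** Suppose log(follow-up/baseline) is normal with median ratio *g* and SD *s*. Then

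- median % change = 100(g - 1)
- mean % change = 100(g·exp(s²/2) - 1)

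| s | exp(s²/2) | g = 1 (no median change) | g = 0.5 (median halves) |
|---|---|---|---|
| 0.5 | 1.133 | +13% | -43% |
| 0.75 | 1.325 | +32% | -34% |
| 1.0 | 1.649 | +65% | -18% |
| 1.25 | 2.184 | +118% | +9% |
| 1.5 | 3.080 | +208% | +54% |

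The mean turns positive when s > √(-2 ln g). For g = 0.5 that is √(2 × 0.693) = 1.18. For a 30% median fall (g = 0.7) it is 0.845.

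**2. Does the median protect the reader?** Simulation with 40,000 replicates, n = 40 in the arm and a true median fall of 30%:

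| s | P(observed mean % change > 0) | P(observed median % change > 0) |
|---|---|---|
| 0.5 | 0.3% | <0.1% |
| 0.75 | 26% | 0.7% |
| 1.0 | 73% | 3.4% |
| 1.25 | 93% | 7.4% |

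The median seldom points the wrong way; the mean often does once *s* reaches about 0.75.

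**3. Raw change.** If baseline and follow-up are lognormal with log SDs s₀ and s₁, the ratio of arithmetic means is g·exp((s₁² - s₀²)/2). With s₀ = s₁ it equals *g*: a ratio of medians of 0.70 gives a ratio of means of 0.70. A mean rise needs the spread to widen. For example, s₀ = 0.8 and s₁ = 1.2 gives 0.7 × exp(0.40) = 1.04.

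**4. Comparing arms by eye.** If *s* is the same in both arms, the factor exp(s²/2) cancels. At s = 1.5, an active arm whose median halves has mean ratio 1.54 and an unchanged placebo arm has 3.08, and 1.54/3.08 = 0.50, the true ratio. This holds in expectation only. The relative standard error of one arm's mean ratio is √((exp(s²) - 1)/n). At n = 40 that is √(0.284/40) = 8% for s = 0.5, √(1.718/40) = 21% for s = 1.0 and √(8.488/40) = 46% for s = 1.5.

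**5. What a log-scale comparison would deliver.** Without baseline adjustment, SE = s·√(1/40 + 1/40), and the 95% CI is the estimated ratio multiplied or divided by exp(1.96·SE).

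| s | CI factor, 40 vs 40 | Power at true ratio 0.70, 40 vs 40 | CI factor, 80 vs 40 | Power at true ratio 0.70, 80 vs 40 |
|---|---|---|---|---|
| 0.5 | 1.24 | 89% | 1.21 | 96% |
| 0.75 | 1.39 | 57% | 1.33 | 69% |
| 1.0 | 1.55 | 36% | 1.46 | 45% |
| 1.25 | 1.73 | 25% | 1.61 | 31% |

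Power is at two-sided 0.05. Missing samples are not allowed for.

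**The case against.** The strongest defence is that this is a considered choice. Protocol and SAP agree on descriptive pharmacodynamics, the study is Phase 2 with no formal sample size, and the objective is only to examine effects. A model would often be imprecise: at 40 against 40, power for a 30% reduction is 57% or less once *s* reaches 0.75. This stands against calling the plan contradictory or asking for a powered test. It does not explain why a stated secondary objective gets no estimate when the SAP already has a suitable model for continuous efficacy endpoints.

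Four stronger readings are tempting, and the documents do not support them:

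- **That only means will be shown.** SAP 3.5 does not restrict the summary, and SAP 3.1.4 generally includes the median.
- **That skew alone can make mean raw change rise while the typical subject improves.** Step 3 shows that the spread must also widen after baseline, and the documents give no information on that.
- **That the objective cannot be answered at all.** The tables are by arm and include placebo, and with equal spread the distortion of the mean cancels in expectation (step 4). What is lost is a direct estimate, its precision and its interval.
- **That the gap concerns all seven markers equally.** Five of them are exploratory.

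**Conclusion.** The concern holds as a moderate weakness in the choice of analysis. For CRP and D-dimer, the plan provides no razuprotafib-placebo estimate, interval, baseline adjustment or log-scale analysis. That conclusion comes from the text and needs no assumption.

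The point about mean percentage change is secondary and conditional. It rests on a lognormal model and an assumed *s*. At s = 0.5 the distortion is small and no sign reversal arises for a marker that halves; at s = 1.5 it is large. It misleads only a reader who ignores the median, so the mean percentage change need not be dropped.

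**What to change.** In SAP 3.5, keep the descriptive tables, say explicitly that medians are shown, and add geometric means. Then add:

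- **Model.** For CRP and D-dimer, an ANCOVA of the log Day 7 (or discharge) value with treatment, log baseline and disease severity. Apply the same model to the other five markers, labelled exploratory.
- **Output.** The geometric mean ratio against placebo with 95% CI, for each dose and for pooled doses. Label it as estimation; any p-values are nominal.
- **Coverage.** State that the analysis includes only subjects with both a baseline and a Day 7 or discharge sample. The worst-outcome rule for deaths in SAP 3.1.6 is written for efficacy endpoints, so it does not fill these gaps.
- **Low values.** State how results below the quantification limit enter the log scale.

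The samples are already scheduled in Protocol 7.3, so the cost is a small programming effort. The drawback is the wide intervals in step 5, which should be presented as such. The text should be in place before database lock; a comparison added later would be read as post hoc, the label that SAP 3.4 gives to additional efficacy and safety analyses.

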3.6 Safety Assessment

Safety data will be summarized based on the Safety Population. Safety will be determined by evaluating clinical laboratory findings (blood chemistry, hematology, and coagulation), vital signs (blood pressure, heart rate, SpO₂ [for non-ventilated subjects only], and respiratory rate), 12-lead electrocardiograms, and AEs reported during the study.

3.6.1 Adverse Events (AEs)

AEs, which include clinical laboratory test variables, will be monitored and documented from the time of the first dose of study drug until Day 28. All AEs will be coded to system organ class and preferred term using MedDRA version 23.0. Treatment-emergent adverse events (TEAEs) will be defined as an event that occurs on or after the first dose of study drug.

An overview of AEs will be provided including counts and percentages of subjects and event counts with the following:

- Any TEAEs (Overall, by maximum severity)
- Any study drug related TEAEs
- Any treatment-emergent serious AEs (TESAEs)

- Any TEAEs leading to discontinuation of study drug
- Any TEAEs leading to death

Counts and percentages of subjects and event counts will also be presented by system organ class and preferred term for each of the categories in the overview.

All AEs will be displayed in listings. In addition, listings will be presented specifically for SAEs and TEAEs leading to discontinuation of study drug.

3.6.2 *Clinical Laboratory Tests*

Values and changes from baseline of clinical laboratory variables for blood chemistry, hematology, and coagulation will be summarized using descriptive statistics by treatment group and time point. The number of available observations and out-of-range values (absolute and in percentage) will also be presented by treatment group. Clinical Laboratory data will be listed.

3.6.3 *Vital Signs*

Vital signs will include blood pressure, heart rate, SpO2 (for non-ventilated subjects only), and respiratory rate. Temperature will be measured at Screening only.

Values, changes from baseline, changes from pre-dose for each TID dose of vital signs will be summarized using descriptive statistics by treatment group and time point. Vital signs will be listed.

3.6.4 *Electrocardiograms*

Values and changes from baseline of electrocardiograms data will be summarized using descriptive statistics by treatment group and time point (baseline and Day 7). The overall interpretation will be summarized by counts and percentages by treatment group and total. 12-lead electrocardiograms data will be listed.

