4.2 Exclusion Criteria

Subjects who meet any of the following criteria will be excluded from participation in the study:

1. Inability to initiate study drug within 12 hours after randomization;
2. Female of childbearing potential who is unable or unwilling to forego breastfeeding through Day 28;
3. Systolic blood pressure < 100 mmHg;
4. In shock or requiring pressor support;
5. Subjects who are on invasive mechanical ventilation; are receiving oxygen delivered by extracorporeal membrane oxygenation (ECMO); or have clinical need for 1 of the preceding therapies, but preceding therapies not able to be administered in setting of resource limitation;
6. Alanine aminotransferase (ALT) or aspartate aminotransferase (AST) $> 3 \times$ the upper limit of normal (ULN);
7. Total bilirubin $> 2 \times$ ULN;
8. Estimated glomerular filtration rate < 30 mL/min or receiving hemodialysis or hemofiltration;
9. Moribund subject not expected to survive 24 hours in the opinion of the treating clinical team;
10. Any concurrent serious medical condition (eg, active malignancies on chemotherapy, post-organ transplant, end stage congestive heart failure) or not likely to respond to treatment;
11. Decision to withhold life-sustaining treatment;

Note: In the event of cardiac arrest, the decision to withhold cardiopulmonary resuscitation only does not fulfill this exclusion criterion.

12. Use of sensitive substrates of cytochrome P450 (CYP) 2C8 (eg, repaglinide, paclitaxel, or cerivastatin);
13. Use of CYP2C8 inhibitors (eg, gemfibrozil, fluvoxamine, or ketoconazole);
14. Participation in another investigational study during the present study through the last visit (Day 28); or
15. Previous randomization in this study.

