4.4 Stopping Criteria

4.4.1 Criteria for Discontinuation of Study Drug in Individual Subjects

Subjects will be discontinued from study drug, but will continue to be followed in the study, if they experience any of the following:

- \geq Grade 3 (Common Terminology Criteria for Adverse Events [CTCAE] version 5.0) AE or clinically significant laboratory abnormality considered related to study drug;
- \geq Grade 3 (CTCAE version 5.0) injection reaction in the first 24 hours post-injection;
- Significant drop in the subject's blood pressure such that medical intervention is necessary (ie, \geq Grade 3 [CTCAE version 5.0] AE), a blood pressure $<80/60$ that is considered related to study drug, or lack of response to simple measures such as postural change (eg, supine with legs raised) or oral or intravenous bolus; and/or
- Anaphylactic reaction that is moderate or severe, or any anaphylactic reaction that requires emergency medical management.

For any subject who prematurely discontinues from study drug, the reason and date of discontinuation will be documented in the source and electronic case report forms (eCRFs). The subject should continue to complete all safety assessments at subsequent study visits up to and including Day 28.

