Clinically significant abnormal laboratory or other examination findings that are detected during the study or are present at the date of the first dose of study drug and significantly worsen during the study should be reported as AEs, as described below. The Investigator will exercise his or her medical and scientific judgment in deciding whether an abnormal laboratory finding or other abnormal assessment is clinically significant. Clinically significant abnormal laboratory values occurring during the clinical study will be followed until repeat tests return to normal, stabilize, or are no longer clinically significant. Abnormal test results that are determined to be an error should not be reported as an AE. Laboratory abnormalities or other abnormal clinical findings should be reported as an AE if any of the following are applicable:

- If an intervention is required as a result of the abnormality;
- If action taken with the study drug is required as a result of the abnormality; or
- Based on the clinical judgment of the Investigator.

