8.8 Clinical Laboratory Evaluations

Samples for blood chemistry, hematology, and coagulation will be obtained as indicated in [Appendix A](#). See [Appendix B](#) for a complete list of analytes. If a blood chemistry, hematology, or coagulation assessment was performed within 24 hours prior to the first dose of study drug, it is not necessary to repeat the assessment on Day 1. Effort should be made to obtain blood chemistry, hematology, and coagulation at approximately the same time on each day indicated in [Appendix A](#); however, it should not be considered a protocol deviation if this is not possible. After the Treatment Period, blood chemistry, hematology, and coagulation will be assessed weekly until Day 28, unless discharged. All safety clinical laboratory evaluations will be performed at the local laboratory as indicated in [Appendix A](#).

A local urine pregnancy test will be performed for females of childbearing potential only at Screening.

Arterial blood gas should be obtained locally only if clinically indicated. If arterial blood gas is obtained, the subject's current oxygen requirement should also be recorded.

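### SAP 3.6.2 counts out-of-range laboratory values rather than affected subjects and plans no shift table, so new abnormalities are not separated from those present at baseline

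*SAP*

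**What the plan says.** SAP 3.6.2 plans three laboratory outputs:

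- "Values and changes from baseline of clinical laboratory variables for blood chemistry, hematology, and coagulation", to be described for each arm at each visit;
- for abnormal results, a count and share: "The number of available observations and out-of-range values (absolute and in percentage) will also be presented by treatment group";
- a record of individual results: "Clinical Laboratory data will be listed".

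The second output is the one at issue. Its unit is the laboratory value. It names no time point and does not say whether pre-dose values are included or how several values from one subject are handled. The section plans no shift table, no worst post-baseline value and no CTCAE grading of laboratory results.

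Three protocol features bear on this:

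- **Eligibility (4.2).** Exclusion starts only above 3 x ULN for ALT or AST, above 2 x ULN for "Total bilirubin", and below 30 mL/min for estimated GFR. Lesser abnormalities are admitted.
- **Schedule (8.8 and Appendix A).** Panels fall at Screening and on Days 1, 3, 5 and 7. Then: "After the Treatment Period, blood chemistry, hematology, and coagulation will be assessed weekly until Day 28, unless discharged". A subject who leaves before Day 7 has the Day 7 panel on the day of discharge (footnote c). Extended dosing adds daily panels from Day 8 (footnote r).
- **Individual stopping (4.4.1).** The first criterion works by subject and CTCAE grade: Grade 3 or above for an "AE or clinically significant laboratory abnormality considered related to study drug".

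Laboratory findings also have a route into the adverse event tables. SAP 3.6.1 says "AEs, which include clinical laboratory test variables, will be monitored and documented", and Protocol 8.1 requires AE reporting of "Clinically significant abnormal laboratory or other examination findings that are detected during the study" and of baseline findings that worsen significantly.

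**The concern.** Safety is a primary objective. The reader of a laboratory safety table wants to know how many subjects in each arm became abnormal, or more abnormal, on drug. A percentage of out-of-range values does not answer that. A subject who entered with a raised ALT and keeps it adds to the count at every panel. A subject who stays in hospital adds more values than one who leaves early. With 7-day dosing, three of the long-stay subject's panels (Days 14, 21 and 28) fall after dosing has ended.

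At stake is how well the final report shows a between-arm difference in new laboratory abnormalities. The difference may be diluted. Under some conditions it may point the wrong way.

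**Working it through.** The documents give no figure on this point, so there is nothing to reproduce. The check has two parts.

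**1. Scheduled panels per subject (Appendix A with footnotes c, g and r)**

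| Course | Panels incl. Screening and Day 1 | Panels after Day 1 |
|---|---|---|
| Discharged Day 4 | 4 (Screening, Days 1, 3, 4) | 2 |
| In hospital to Day 28, 7-day dosing | 8 (Screening, Days 1, 3, 5, 7, 14, 21, 28) | 6 |
| In hospital to Day 28, 14-day dosing | 14 (Days 8 to 13 added) | 12 |

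The weight ratio of long to short stay is 8/4 = 2 over all panels and 6/2 = 3 after Day 1. With 14-day dosing it is 14/4 = 3.5 and 12/2 = 6. Each total falls by one if the Day 1 panel is waived because of a test in the preceding 24 hours.

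**2. Effect on a pooled percentage (illustration)**

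Only the panel counts and the arm size come from the documents (Part 2: 120/3 = 40 per arm under 1:1:1). Everything else is assumed: short stay means discharge on Day 4, long stay means in hospital to Day 28, 7-day dosing, a baseline abnormality persists, and a new abnormality is present on every panel after Day 1.

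Let b be the share abnormal at baseline and e the share of baseline-normal subjects who become abnormal. Abnormal values per subject are 4b + 2(1 − b)e for short stay and 8b + 6(1 − b)e for long stay. The pooled share is the sum of these over subjects, divided by all values.

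*Equal stay (20 short, 20 long per arm; 20 x 4 + 20 x 8 = 240 values), e = 10% control and 20% drug:*

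| b | Control | Drug | Ratio |
|---|---|---|---|
| 20% | (48 + 12.8)/240 = 25.3% | (48 + 25.6)/240 = 30.7% | 1.21 |
| 40% | (96 + 9.6)/240 = 44.0% | (96 + 19.2)/240 = 48.0% | 1.09 |
| 60% | (144 + 6.4)/240 = 62.7% | (144 + 12.8)/240 = 65.3% | 1.04 |

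A table of baseline-normal subjects would show 10% v 20%, a ratio of 2.0, in every row.

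*Shorter stay on drug (28 short, 12 long; 28 x 4 + 12 x 8 = 208 values), b = 30% short-stay and 60% long-stay:*

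- Control (20 short, 20 long), e = 10%: (20 x 1.34 + 20 x 5.04)/240 = 127.6/240 = 53.2%.
- Drug, e = 20%: (28 x 1.48 + 12 x 5.28)/208 = 104.8/208 = 50.4%. The direction is reversed.
- Drug, e = 10% (no laboratory effect): (28 x 1.34 + 12 x 5.04)/208 = 98.0/208 = 47.1%. Stay alone moves the figure from 53.2%.
- If b is 40% whatever the stay, with e = 10% in both arms: 44.0% control v (28 x 1.72 + 12 x 3.56)/208 = 90.88/208 = 43.7% drug. The shift nearly vanishes.

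The reversal also needs pre-dose values in the pool. With panels after Day 1 only, the same case gives 91.6/160 = 57.25% control v 73.6/128 = 57.5% drug. The difference is then hidden, not reversed.

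**The case against.** The strongest reply is that this is one supplementary table and the rest of the plan covers most of the ground.

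- **Other outputs.** The preceding sentence of SAP 3.6.2 gives values and changes from baseline by arm and time point, and the SAP's standard summaries include the minimum and maximum. Data are also listed. This stands, although none of these counts affected subjects.
- **Adverse events.** A reader might infer that a Grade 3 change in one or two subjects would be lost. The documents do not support that for clinically significant changes. These are reported as AEs (Protocol 8.1), graded by CTCAE version 5.0 (8.1.3) and tabulated by subject, including by maximum severity (SAP 3.6.1). Two subjects with similar Grade 3 AEs cause the Data Review Committee to convene (Protocol 4.4.2). What remains is that a laboratory value enters this route only if it needs intervention, leads to action on study drug or is judged reportable by the investigator.
- **Time point.** SAP 3.1.3 applies nominal time points to all summaries, SAP 3.1.4 promises clearly defined denominators, and SAP 7 leaves detail to separate programming specifications. Read by time point, each subject has about one value per row, baseline has its own row, and the unequal weighting largely disappears. That reading is open, although the neighbouring sentence names the time point and this one does not. Even so, new onset is not distinguished from persistence, and the scheduled Day 14 to 28 rows hold only inpatients.
- **Dose escalation.** A reader might infer that escalation rests on this table. Escalation follows committee review of safety and PK data as its Charter defines. Nothing ties that review to this percentage.
- **Bias between arms.** Unequal weighting alone does not create it, as the 44.0% v 43.7% result shows. Stay must differ by arm and abnormality must go with stay.

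**Conclusion.** The point holds as a minor weakness in descriptive safety reporting. On either reading of SAP 3.6.2, the out-of-range summary does not show how many subjects developed a new or worse abnormality. If pooled over time, it gives a subject in hospital to Day 28 two to six times the weight of a Day 4 discharge, depending on dosing duration and whether pre-dose panels count. Under the stated assumptions it shrinks a true ratio of 2.0 to between 1.04 and 1.21. It can reverse the direction if pre-dose values are pooled, stay is shorter on drug and sicker subjects stay longer.

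The sizes rest on assumed abnormality rates and lengths of stay. Eligibility permits abnormal baselines, but the documents do not say how common they are. The conclusion that a laboratory signal could not be seen anywhere in the plan would go too far: with equal stay even the pooled figure moves in the right direction, and other outputs contribute. Alpha, power and sample size are not affected.

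**What to change.** In SAP 3.6.2, replace the observation-level percentage with the following, per analyte and treatment group:

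- the number and percentage of subjects by worst Treatment Period value against baseline, using CTCAE version 5.0 grade where one is defined and low/normal/high otherwise, with the number of subjects at risk;
- the number of subjects with a treatment-emergent increase to Grade 3 or higher;
- the off-drug period shown separately;
- any out-of-range percentages that are kept, by time point, with pre-dose values apart.

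The cost is SAP wording, routine shift-table programming and some extra tables. No new data are needed. One limitation remains: a worst value still depends on the number of draws. Within the Treatment Period, a full-stay subject has 3 panels after Day 1 (Days 3, 5 and 7) against 2 for a Day 4 discharge. With 14-day dosing it is 10 (Days 3, 5 and 7 to 14) against 2. Report the number of panels per subject by arm alongside the table.
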